#### 10.4.2 Discontinuations

Discontinued subjects are individuals who voluntarily withdraw or are withdrawn from the study by the investigator after exposure to investigational product.

NOTE: Subjects not implanted at the time of surgery (1st operative eye) and the study IOL **did not** touch the eye must be captured as withdrawn.

Subject numbers of discontinued subjects must not be re-used for another subject (i.e., subject replacement is not allowed).

Subjects may discontinue from study or study treatment at any time for any reason. Subjects may also be discontinued from study treatment at any time if, in the opinion of the investigator, continued treatment poses a risk to their health.

The investigator must document the reason for study or treatment discontinuation in the subject's case history source documents.

To ensure the safety of all subjects who discontinue early, investigators must assess each subject and, if necessary, advise them of any therapies and/or medical procedures that may be needed to maintain their health.

# 10.4.3 Subjects with Aborted Implantation and Explanted IOL(s)

Implantation may be attempted twice. After two aborted attempts to implant, meaning the investigational product touched the eye, the eye must be implanted with a nonstudy provided IOL. Refer to Section 9.6.2 for additional information.

If the IOL implantation is attempted and aborted due to device deficiency, then a device deficiency form must be completed and the IOL must be returned to the study sponsor in appropriate safe packaging.

In case an explant is performed: the explanted eye will be followed for safety as routine standard of care for explants of approved IOLs.

# 10.5 Clinical Study Termination

The study sponsor reserves the right to suspend or close the investigational site or suspend or terminate the study in its entirety at any time.

If the clinical study is prematurely terminated or suspended by the study sponsor:

- The study sponsor must:
  - Immediately notify the investigator(s) and subsequently provide instructions for study termination.
  - Inform the investigator and the regulatory authorities of the termination/suspension and the reason(s) for the termination/suspension.
- The investigator must:
  - Promptly notify the IRB/IEC of the termination or suspension and of the reasons.
  - Provide subjects with recommendations for poststudy treatment options as needed.

The investigator may terminate the site's participation in the study for reasonable cause.

Breaking of the masked treatment codes will be done after locking the database.

# 10.5.1 Follow-up of Subjects after Study Participation has Ended

Following this study, the subject will return to their eye care professional for their routine eye care.

#### 11 ADVERSE EVENTS AND DEVICE DEFICIENCIES

#### 11.1 General Information

An AE is any untoward medical occurrence, unintended disease or injury, or untoward clinical sign (including abnormal laboratory findings) in subjects, users, or other persons, whether or not related to the investigational medical device (test product). Refer to the Glossary of Terms for categories of AEs and SAEs.

Figure 11-1 Categorization of All Adverse Events

[figure not shown]
[figure not shown]

Figure 11-2 Categorization of All Serious Adverse Events

#### **Specific Events Relevant to this Protocol**

In addition to reporting all AEs (serious and non-serious) meeting the definitions, the Investigator must report any occurrence of the following as an SAE:

#### **Cumulative (at any visit during the study) Serious Adverse Events:**

- Cystoid macular edema
- Hypopyon
- Endophthalmitis
- Lens dislocation
- Pupillary block
- Retinal detachment
- SSI (excluding posterior capsulotomy)

#### Persistent (still present at conclusion of study) Serious Adverse Events:

- Corneal stromal edema
- Cystoid macular edema
- Iritis
- Elevated IOP requiring treatment

Any other potentially sight-threatening event may also be considered serious based on the judgment of the investigator and should be reported appropriately as delineated in Section 11.4.

#### 11.2 Device Deficiencies

A device deficiency may or may not be associated with subject harm (i.e., ADE or SADE); however, not all ADEs or SADEs are due to a device deficiency. The investigator should determine the applicable category for the identified or suspect device deficiency and report any subject harm separately. Examples of device deficiencies include the following:

- Failure to meet product specifications (e.g., incorrect IOL power)
- IOL and delivery system defect
- Broken IOL optic
- Broken IOL haptic

- Scratched IOL optic
- Unsealed device packaging
- Suspect product contamination (IOL)

# 11.3 Monitoring for Adverse Events

At each visit, after the subject has had the opportunity to spontaneously mention any problems, the investigator should inquire about AEs by asking the standard questions shown below and report as applicable:

- "Have you had any health problems since your last study visit?"
- "Have there been any changes in the medicines you take since your last study visit?"

In addition, changes in any protocol-specific parameters evaluated during the study are to be reviewed by the investigator. Any untoward (unfavorable and unintended) change in a protocol-specific parameter or questions response that is clinically relevant, in the opinion of the investigator, is to be reported as an AE. These clinically relevant changes will be reported regardless of causality.

# 11.4 Procedures for Recording and Reporting

AEs are collected from the time of signing of informed consent. Any preexisting medical conditions or signs/symptoms present in a subject prior to the start of the study (i.e., before informed consent is signed) are not considered AEs in the study and should be recorded in the medical history section of the eCRF.

In addition, aqueous cells and flare, corneal edema, raised IOP, and superficial punctate keratitis are examples of early postoperative findings that are typically observed following ocular surgery. These are not considered AEs if they can be reasonably expected to resolve within 2 weeks and not result in any untoward long term visual outcome impact.

For each recorded event, the ADEs and SAEs documentation must include: date of occurrence, severity, treatment (if applicable), outcome, and assessments of the seriousness and causality. In addition, the investigator must document all device deficiencies reported or observed with study test and comparator products on the Device Deficiency eCRF. The site must submit all available information on ADEs, SAEs, and device deficiencies to the study sponsor immediately as follows:

- All SAEs must be reported immediately (within 24 hours) of the investigator's or site's awareness.
- ADEs that do not meet seriousness criteria and device deficiencies must be reported within 10 calendar days of the investigator's or site's awareness.
- A printed copy of the completed *Serious Adverse Event and Adverse Device Effect and/or Device Deficiency* eCRF must be included with product returns.
- Additional relevant information after initial reporting must be entered into the eCRF as soon as the data become available.
- Document any changes to concomitant medications on the appropriate eCRFs.
- Document all relevant information from discharge summary, autopsy report, certificate of death, etc., if applicable, in narrative section of the Adverse Device Effect (for related AEs) and Serious Adverse Event eCRF.

**Note**: Should the EDC system become non-operational, the site must complete the appropriate paper SAE and ADE and/or device deficiency form. The completed form is emailed to the study sponsor at [contact] according to the timelines outlined above; however, the reported information must be entered into the EDC system once it becomes operational.

Any AEs and device deficiencies for any non-study marketed devices/products will be considered and processed as spontaneous (following the post-market vigilance procedures) and should be communicated to the device's/product's manufacturer as per local requirements. Any AEs and device deficiencies with the test or comparator IP should still be reported in EDC and can enter in the comment the other manufactures product if applicable.

Study sponsor representatives may be contacted for any protocol related questions and their contact information is provided in the MOP that accompanies this protocol.

Further, depending upon the nature of the AE or device deficiency being reported, the study sponsor may request copies of applicable portions of the subject's medical records. The investigator must also report all AEs and study IP device deficiencies that could have led to a SADE according to the requirements of regulatory authorities or IRB/IEC.

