Serious Health Threat	Signal from any adverse event or device deficiency that indicates an imminent risk of death or a serious deterioration in the health in subjects, users, or other persons, and that requires prompt remedial action for other subjects, users, or other persons.  Note: This would include events that are of significant and unexpected nature such that they become alarming as a potential serious health hazard or possibility of multiple deaths occurring at short intervals.
Study Start	The start of the study is considered to coincide with the enrollment of the first patient.
Study Completion	The completion of the study is considered to coincide with the study-level last subject last visit or the decision to terminate the trial, whichever is later.
Unanticipated Serious Adverse Device Effect (USADE)	Serious adverse device effect which by its nature, incidence, severity, or outcome has not been identified in the risk assessment.
Use Error	User action or lack of user action while using the medical device that leads to a different result than that intended by the manufacturer or expected by the user.

	Note:
	
 
a) Use error includes the inability of the user to complete a task.
 
b) Use errors can result from a mismatch between the characteristics of the user, user interface, task, or use environment.
 
c) Users might be aware or unaware that a use error has occurred.
 
d) An unexpected physiological response of the patient is not by itself considered a use error.
 
e) A malfunction of a medical device that causes an unexpected result is not considered a use error.
 

Vulnerable Subject	An individual who is unable to fully understand all aspects of the investigation that are relevant to the decision to participate, or who could be manipulated or unduly influenced as a result of a compromised position, expectation of benefits or fear of retaliatory response.

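### Section 11.4 allows 10 calendar days for every device deficiency, with no faster sponsor notification for those that could have caused a serious device effect or that signal a Serious Health Threat

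*Protocol*

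**What the plan says.** Protocol Section 11.4 opens its reporting rules with "The site must submit all available information on ADEs, SAEs, and device deficiencies to the study sponsor immediately as follows". Two time limits follow. For serious events: "All SAEs must be reported immediately (within 24 hours) of the investigator's or site's awareness". For the rest: "ADEs that do not meet seriousness criteria and device deficiencies must be reported within 10 calendar days of the investigator's or site's awareness". In that second rule the seriousness condition attaches to ADEs only; the part that reads "device deficiencies must be reported within 10 calendar days" carries no condition.

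Two other places recognise an urgent kind of deficiency. The glossary (Section 1) defines a Serious Health Threat as "Signal from any adverse event or device deficiency that indicates an imminent risk of death or a serious deterioration in the health" of subjects, users or others, and adds that it calls for quick corrective action to protect other people. Later in Section 11.4 the investigator must also report "study IP device deficiencies that could have led to a SADE according to the requirements of regulatory authorities or IRB/IEC".

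Section 11.2 states that a deficiency may occur with or without harm to the subject, and that harm is reported separately. Its examples include suspected contamination of the lens and unsealed packaging. Section 7.5 provides for no data monitoring committee.

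**The concern.** A deficiency noticed before anyone is hurt is the signal that lets the sponsor protect other subjects. The sponsor supplies the lenses (Section 9.1) and deals with all of the approximately 10 sites, so it is the party placed to warn the others. Under Section 11.4 a site that suspects lens contamination, with no injury so far, complies fully by telling the sponsor on day 10. That is hard to square with a glossary entry that treats some deficiencies as needing quick action, and with a lead-in that asks for immediate submission. Subject safety between site awareness and sponsor awareness is at stake. The primary endpoint and its analysis are not affected.

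**Working it through.** The 10 days is a procedural rule, so there is no plan figure to reproduce. The check is to set the texts side by side and then give a rough scale.

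**Which deficiencies fall in the gap**

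1. *Deficiency with serious harm.* Section 11.2 has the harm reported separately, and Section 11.4 gives SAEs 24 hours. No gap.
2. *Deficiency leading to a medical or surgical intervention to prevent serious harm.* The glossary's SAE definition, item d, counts this as an SAE and includes any ocular secondary surgical intervention except posterior capsulotomy. A preventive lens exchange is therefore a 24-hour event. No gap.
3. *Deficiency with neither.* Only the 10-day rule applies. The later sentence in Section 11.4 on SADE potential points to regulator or IRB/IEC requirements; it gives no time limit and does not name the sponsor as recipient, so it does not shorten the 10 days. The visible text of Section 11 never uses the term Serious Health Threat. Section 10.4.3, on implantations aborted for a deficiency, asks for a form and return of the lens, again with no shorter limit. This is the gap.

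**Scale, for illustration only**

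Inputs: 132 implanted subjects, about 6 months of recruitment and about 10 sites (Section 8); about 66 subjects per sub-study (Section 7.1). Assumptions: implantations spread evenly over the recruitment period, sites of equal size, and a month of 365.25/12 days. The 4- and 12-month rows are an assumed range.

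- Eyes: 132 × 2 = 264.
- Implantations per day = 264 / accrual days.
- Other sites' share = 9/10.

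| Accrual | Days | Per day | 10 days, all sites | 10 days, other sites |
|---|---|---|---|---|
| 4 months | 121.8 | 2.17 | 21.7 | 19.5 |
| 6 months | 182.6 | 1.45 | 14.5 | 13.0 |
| 12 months | 365.2 | 0.72 | 7.2 | 6.5 |

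At 6 months the comparable 24-hour figure for the other sites is 1.45 × 0.9 = 1.3. These counts pool all three lens models. For one test model, 66 eyes / 182.6 days × 10 days = 3.6 implantations across all sites.

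**The case against.** The strongest reply is that the text permits delay but does not direct it: immediate submission is the stated expectation and 10 days the outer limit. That stands, and it is why continued implantation elsewhere is only possible.

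The second reply is that a shorter timeline may sit outside these documents. The glossary makes the manual of procedures part of the clinical investigation plan, Section 14 binds the study to ISO 14155 and to IRB/IEC and regulator conditions, and Figures 11-1 and 11-2 are not shown. A reader might infer that no faster route exists anywhere; the documents do not establish that. They do show that the only site-to-sponsor timelines they state are those in Section 11.4. The glossary also does not say that the site decides what is a Serious Health Threat.

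Three other stronger readings are tempting and not supported:

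- *That the 24-hour rule covers only harm already done.* It also covers interventions to prevent serious harm.
- *That the same subject's second eye is exposed because it follows 7 to 14 days after the first.* The 10 days run from the site's own awareness, so the site treating that subject already knows. The second eye also receives a different lens model (Section 9.3).
- *That all 14 to 15 implantations in 10 days share the defect.* That count includes the reporting site and pools three models over a range of powers, and the documents say nothing about lots.

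**Conclusion.** The point holds in this limited form. Section 11.4 places every device deficiency on a 10-calendar-day limit, including those its own later sentence and the glossary mark out as potentially serious or urgent. The gap concerns deficiencies with neither serious harm nor a preventive intervention so far. Its effect is possible late sponsor awareness. The scale is about 13 study-lens implantations at the other sites in 10 days, or about 7 to 20 over the assumed accrual range; for a single test model it is 3 to 4 across all sites at 6 months. These are counts of implantations, not of eyes exposed to a common defect, and they rest on even accrual and equal sites. The change should be made: the texts do not fit together and the repair is small.

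**What to change.** Reconcile the glossary entry with the two parts of Section 11.4 by splitting the second reporting bullet:

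- Device deficiencies that had the potential to cause a SADE, or that meet the Serious Health Threat definition, go to the sponsor on the existing 24-hour SAE timeline.
- All other device deficiencies, and non-serious ADEs, stay at 10 calendar days.

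Add a matching tick-box to the existing Device Deficiency eCRF, and align any timeline in the manual of procedures. Design, endpoints and analysis do not change. The cost is more expedited reports, possibly more than a few: several Section 11.2 examples, such as incorrect lens power, a broken haptic or a scratched optic, could plausibly lead to a secondary surgical intervention and so qualify. A short note in the manual on which deficiencies count as having SADE potential would help sites apply the split consistently.

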# 11.5 Intensity and Causality Assessments

Where appropriate, the investigator must assess the intensity (severity) of the AE based on medical judgment with consideration of any subjective symptom(s), as defined below:

#### Intensity (Severity)

Mild: An AE is mild if the subject is aware of but can easily tolerate the sign or symptom.

Moderate: An AE is moderate if the sign or symptom results in discomfort significant enough to cause interference with the subject's usual activities.

Severe: An AE is severe if the sign or symptom is incapacitating and results in the subject's inability to work or engage in their usual activities.

For every AE in the study, the investigator must assess the causality (related or not related to the medical device or study procedure). An assessment of causality will also be performed by study sponsor utilizing the same definitions, as shown below:

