# 1 GLOSSARY OF TERMS

Names of Test Product(s)	Throughout this document, test product(s) will be referred to as Clareon PanOptix Pro, Model PXYWT0 and Clareon PanOptix Pro, Model PAYWT0  When Clareon PanOptix Pro is used it refers to both models independently: Model PAYWT0 or Model PXYWT0
Name of Comparator Product(s)	Clareon PanOptix, Model CNWTT0
Adverse Device Effect (ADE)	Adverse event related to the use of an investigational medical device or comparator.  Note: This definition includes adverse events resulting from insufficient or inadequate instructions for use, deployment, implantation, installation, or operation; any malfunction; and use error or intentional misuse.
Adverse Event (AE)	Untoward medical occurrence, unintended disease or injury, or untoward clinical signs (including abnormal laboratory findings) in subjects, users, or other persons, whether or not related to the investigational medical device or comparator and whether anticipated or unanticipated.  Note: For subjects, this definition includes events related to the investigational medical device, comparator, or the procedures involved. For users or other persons, this definition is restricted to the use of the investigational medical device or comparator.  Requirements for reporting adverse events in the study can be found in Section 11.
Anticipated Serious Adverse Device Effect (ASADE)	An effect which by its nature, incidence, severity, or outcome has been identified in the risk assessment.

Clinical Investigation Plan (CIP)	The document(s) stating the rationale, objectives, design, and prespecified analysis, methodology, organization, monitoring, conduct, and record-keeping of the clinical investigation.  Note: The protocol and other documents referenced in the protocol (for example, the statistical analysis plan, the manual of procedures, the deviations and evaluability plan, and the protocol monitoring plan) comprise the CIP.
Clinical Investigation Report (CIR) / Clinical Study Report	The document describing the design, execution, statistical analysis, and results of a clinical investigation. The clinical investigation report is synonymous with the clinical study
	report.

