#### **Causality**

Related: An AE classified as related may be either definitely related or possibly related where a direct cause and effect relationship with the medical device or study procedure has not been demonstrated, but there is a reasonable possibility that the AE was caused by the medical device or study procedure.

Not Related: An AE classified as not related may either be definitely unrelated or simply unlikely to be related (i.e., there are other more likely causes for the AE).

The study sponsor will assess the AEs and may upgrade the investigator's assessment of seriousness and/or causality. The study sponsor will notify the investigator of any AEs that is upgraded from non-serious to serious or from unrelated to related.

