5.3.1 Adverse Events

The applicable definition of an AE is in the study protocol. All AEs occurring from when a subject signs informed consent to when a subject exits the study will be accounted for in the reporting.

Descriptive summaries (counts and percentages) for AEs will be presented by Preferred Term.

Adverse events will be summarized in the following tables:

- 1. Overall Summary of Treatment-Emergent Adverse Events
- 2. All Adverse Events (Serious and Nonserious Combined)
 - a. Ocular
 - b. Nonocular
- 3. All Serious Adverse Events (including Serious Adverse Device Effects)
 - a. Ocular
 - b. Nonocular
- 4. Subject Listings
 - a. All Ocular
 - b. All Nonocular

In addition, listings of AEs that occur after signing informed consent but prior to exposure to investigational product will be provided separately for ocular and nonocular AEs.

Secondary surgical interventions (SSIs) will be summarized descriptively (counts and percentages) and will be presented separately by lens model in each of the following categories:

- Any
- Related to IOL due to optical properties
- Related to IOL not due to optical properties
- Unrelated to IOL

Additionally, descriptive summaries (counts and percentages) for SSIs will be presented by Preferred Term. Confidence intervals/limits will be presented as applicable.

A listing of all SSIs will also be provided.

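### One causality call covers lens and surgery together, so a purely surgical event can be recorded as an adverse device effect, contrary to the glossary

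*Protocol*

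**What the plan says.** Protocol 11.5 sets a two-level scale: "For every AE in the study, the investigator must assess the causality (related or not related to the medical device or study procedure"). An event is related if "there is a reasonable possibility that the AE was caused by the medical device or study procedure". The sponsor works on the same scale: "An assessment of causality will also be performed by study sponsor utilizing the same definitions". The sponsor may upgrade an event only from unrelated to related.

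Protocol 11.4 says that supporting information goes "in narrative section of the Adverse Device Effect (for related AEs) and Serious Adverse Event eCRF".

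The glossary (Protocol 1) defines an ADE more narrowly: "Adverse event related to the use of an investigational medical device or comparator". Its note widens this a little: "This definition includes adverse events resulting from insufficient or inadequate instructions for use, deployment, implantation, installation, or operation", and also malfunction, use error and intentional misuse. The glossary entry for AE, by contrast, lists the procedures involved alongside device and comparator. A SADE is an ADE with a serious outcome, and a USADE is a SADE not identified in the risk assessment.

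SAP 5.3.1 tabulates all AEs, and then "All Serious Adverse Events (including Serious Adverse Device Effects"). It splits SSIs by whether they relate to the IOL. It specifies no such split for other AEs.

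**The concern.** Both eyes of every subject have cataract surgery, so surgical events are expected with either lens. The safety question is about the lens: Protocol 5.3 describes the Pro models as an incremental change to the comparator. A causality scale that joins lens and surgery with an "or" cannot answer that question, because both kinds of event get the same code.

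The class has consequences. Non-serious ADEs must be reported within 10 calendar days (11.4). SADE and USADE status build on ADE status. Section 11.4 also requires onward reporting of events that could have led to a SADE, and 11.6 asks for return of products linked to product-related AEs, a category that the 11.5 scale does not produce. With about 10 sites, one site following 11.4 and 11.5 literally and another following the glossary would classify the same event differently, and both could claim to comply.

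**Working it through.** The plan states no figure on this point, so there is none to reproduce. The check sets the passages side by side and then illustrates size with assumed rates.

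**Step 1. Trace one event.** Take iris trauma during surgery, which Protocol 5.3 lists as a possible problem, with no fault in the lens, its instructions or its use.

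| Source | Question asked | Result |
|---|---|---|
| Protocol 11.5 | Possibly caused by device or procedure? | Yes: related |
| Protocol 11.4 | Which form takes related AEs? | ADE eCRF |
| Protocol 1, ADE | Related to use of test or comparator device? | No |
| Protocol 1, ADE note | Inadequate instructions, malfunction, use error or misuse? | No |

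The first two rows and the last two disagree. Because the AE entry in the glossary names procedures and the ADE entry does not, the protocol itself treats the two causes as distinct.

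**Step 2. Find the affected outputs.**

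- Affected: any count or report confined to related AEs, ADEs, SADEs or USADEs.
- Not affected: the SAP 5.3.1 tables of all AEs and all SAEs, which have no causality filter and are by Preferred Term, with ocular events by lens model (SAP 2.2); the SSI table; and the BCDVA analysis.

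**Step 3. Size, on assumed rates.** About 66 eyes per lens in each sub-study (Protocol 7.1). Let p be the lens-caused rate and q a surgical rate common to both lenses, with the two causes independent.

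- Rate in the combined class: P = 1 − (1 − p)(1 − q)
- Difference: (p_test − p_comp)(1 − q)
- SE = √{[P_test(1 − P_test) + P_comp(1 − P_comp)] / 66}, treating eyes as independent and so ignoring the pairing

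For p = 10% v 3% and q = 10%: 1 − 0.90 × 0.90 = 0.190; 1 − 0.97 × 0.90 = 0.127; difference 0.063; ratio 0.190/0.127 = 1.50. In eyes: 0.190 × 66 = 12.5 v 0.127 × 66 = 8.4, against 0.10 × 66 = 6.6 v 0.03 × 66 = 2.0 if kept apart.

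| q | Combined rates | Difference | Ratio | SE | Difference/SE |
|---|---|---|---|---|---|
| 0 (kept apart) | 10.0% v 3.0% | 0.070 | 3.33 | 0.043 | 1.65 |
| 5% | 14.5% v 7.9% | 0.067 | 1.85 | 0.055 | 1.22 |
| 10% | 19.0% v 12.7% | 0.063 | 1.50 | 0.063 | 0.99 |
| 20% | 28.0% v 22.4% | 0.056 | 1.25 | 0.075 | 0.74 |
| 30% | 37.0% v 32.1% | 0.049 | 1.15 | 0.083 | 0.59 |

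Other assumed lens-caused rates behave alike. For 6% v 2% the ratio falls from 3.0 to 1.31 at q = 10% and 1.09 at q = 30%. For 15% v 3% it falls from 5.0 to 1.85 and 1.26.

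The absolute difference shrinks only by the factor 1 − q, that is by 5% to 30% here. The ratio falls much more, and the standard error grows.

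**The case against.** The strongest reply is that loose wording is not a classification rule. No sentence says that every AE rated related is an ADE. The glossary still governs, and 11.1 sends the reader to it. The words about related AEs are a parenthesis in a bullet on where to file discharge summaries and similar records. Figures 11-1 and 11-2, which categorize AEs and SAEs, were not available in the text examined, and the eCRF and manual of procedures may already hold separate fields. All of this stands. A reader might infer that surgical events *become* ADEs under the plan; the documents support only that they *can be recorded* so.

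A reader might also infer that any lens difference in safety will be diluted. The documents do not support that. The SAP names no table of related AEs or ADE rates. All AEs and SAEs are shown whatever the causality call. SSIs are split by relation to the IOL. Surgical problems, device deficiencies, PCO, capsulotomy and IOL observations are tabulated by lens model. There are no safety hypotheses, so no test or decision rule is at risk.

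Nor would every surgical finding be caught. Section 11.4 excludes typical early postoperative findings, such as cells and flare, that should clear within 2 weeks without lasting visual effect. The glossary note already brings some implantation-related events within ADE.

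What the reply does not meet is the scale itself. As written, neither investigator nor sponsor can record under 11.5 that surgery, and not the lens, caused an event.

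**Conclusion.** The point holds as an inconsistency between Protocol 11.4 and 11.5 and the glossary. The stated causality data cannot separate lens-caused from surgery-caused events, and a literal reading allows a purely surgical event onto the ADE form. The reach is limited to related-AE, ADE, SADE and USADE classification, counts and reporting.

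Within that reach the effect is added noise. Surgery is common to both eyes and the lens for the first eye is randomized, so the extra events should fall about equally on the two lenses and favour neither, while the ratio moves toward 1. The sizes shown rest wholly on assumed rates, independence of the two causes, and eyes treated as independent. The primary conclusion on BCDVA does not depend on this. It is worth correcting because the change is cheap and ADE status carries reporting duties.

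**What to change.** 1. In Protocol 11.5, replace the single call with two yes/no judgments for each AE: related to the lens, and related to the study procedure. Apply both to the investigator's and the sponsor's assessment.
2. In Protocol 11.4, state that ADE and SADE status follows the device judgment as the glossary defines it, including its note on inadequate instructions, malfunction and use error. Amend the parenthesis on the ADE eCRF to match.
3. In SAP 5.3.1, state that SADEs are identified by that judgment and shown by lens model.

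The cost is one more judgment per AE, an eCRF field if none exists, and a few sentences. If the eCRF already records both, only the wording changes. Some events at the edge of the glossary note, such as those from implantation technique, will still need case-by-case judgment.
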